9.3.2. Follow-up

Once an AE is detected, it must be proactively followed until its resolution or 30 days after the last study treatment administration. After this visit and until day 90 after last administration of study treatment non-serious treatment-related Aes and all SAEs have to be followed. Ongoing SAEs at the 90-day safety follow-up phone call must be followed up until stabilization or until the outcome is known, unless the patient is documented as “lost to follow up”.

In addition, any significant AE as recommended by Transgene must be followed until it is resolved or stable or returned to baseline status.

Transgene or its representative reserves the right to ask for further information on any AE/SAE that may be considered of interest or when the event is not previously documented in the IB (new occurrence) and is thought to be related to the study treatment.

9.3.3. Documentation

All AEs/SAEs will be reported in the source document with at least the nature, the date of onset and end, the causality, and the treatment (if applicable).

Copies of SAE form will be filed in the Investigator Site File along with copies of any correspondence with the Independent Ethics Committee (IEC). The Investigator Site File will also include copies of notification letters and/or faxes with forms sent to Health Authorities and Gene Therapy Bodies if appropriate.

9.4. Reporting of DLTs during the phase Ib of the study

During the phase Ib of the study, Transgene must be informed **immediately by the center** of the occurrence of any DLT occurring within the first 4 weeks of study treatments in all patients included in the phase Ib of the study.

The following action must be undertaken by the investigators on occurrence of any AE that fulfill the criteria for a DLT:

- The Investigator must inform Transgene and duly complete the appropriate eCRF form even if the data are incomplete or if it is obvious that more data will be needed.
- The following information must be present: description of the AE, intensity and relationship to study drugs, date of onset, status at the time of reporting, action taken on study treatments.
- Transgene may request any additional information (copies of reports, lab tests etc.,) to the center in order to better assess the DLT.

9.5. Serious Adverse Event / Serious Adverse Reaction / Suspected Unexpected Serious Adverse Reaction notification

Reporting to Transgene

Any SAE occurring during the course of the study (from the signature of ICF and up to 90 days after last study treatment administration whether or not related to the IMP(s) MUST be reported to Transgene. The Investigator must complete and fax a “Serious Adverse Event Form” to Transgene within a maximum of 24 hours of occurrence or knowledge of the event.

France	
Pharmacovigilance Physician	
[REDACTED]	[REDACTED]

An Investigator designee may complete the SAE form, however, the Investigator must sign it. The form can be sent to Transgene with the designee's signature if the Investigator's signature

cannot be obtained within one working day. The Investigator's signature must be obtained as soon as possible, as well as his/her evaluation of the relationship to the IMP(s). The signed form must be faxed to Transgene immediately.

The SAE form should be completed in English.

Follow-up information (e.g., complications or progression of the initial SAE) must be notified to Transgene by the Investigator within the same time frame as the initial SAE form by using a new "SAE form" with the box "follow-up" ticked and sent to Transgene. The follow-up information should describe whether the event has resolved or continues, if and how it was treated and whether the patient continued or withdrew his/her consent.

Transgene or its representative may request further information as needed.

All SAE will be followed to resolution or stabilization.

Notification to Regulatory Authorities / Gene Therapy Bodies / Ethics Committee

Transgene will be solely responsible for regulatory reporting of SUSAR and any other SAEs to Regulatory Authorities, IEC(s) / IRB(s) and Gene Therapy Bodies as per local regulations.

Transgene will also be responsible for reporting SAEs to Ethics Committees (Ecs) and Investigators in accordance with local regulations/requirements.

In case of SUSAR, Transgene will inform all investigators involved in any study with TG4001 that such an event has been reported.

The Investigator is responsible for informing IRB(s) of SUSARs, any other SAEs and any follow-up information as per local regulations.

Transgene is responsible for ensuring that all AEs and SAEs that are observed or reported during the study are collected and reported to the FDA in accordance with CFR 312.32 (IND Safety Reports).

Transgene will transmit SAEs to Merck KgaA and Pfizer for **all** initial or follow-up reports and any safety information originating from this Study within the timelines and formats specified in and in accordance with the Safety Data Exchange Agreement.

Merck KgaA / EMD Serono and Pfizer will each cross-report SUSARs from the Study associated with avelumab to national Regulatory Authorities of countries where they are Sponsors of clinical trials with avelumab and where such cross-reporting is required per applicable regulations.

9.6. Special situations

Any clinical AE with severity of Grade 4 must be reported as an SAE; however, a laboratory abnormality of Grade 4, such as anemia or neutropenia, is considered serious only if the condition meets one of the serious criteria described above (see Section 9.1).

Pregnancy

Study treatments must be discontinued immediately when a patient becomes pregnant.

The occurrence of a pregnancy must be reported to Transgene by the Investigator using a “Pregnancy form”:

- The first part of the form is used to collect information at the beginning of the pregnancy. It should be completed and reported as soon as possible and within 24 hours of knowledge
- The second part of the form is to collect information about the outcome of the pregnancy. It should be reported within the same time frame and even if the patient was withdrawn from the study

Pregnancies have to be followed up to the completion or termination of the pregnancy, collecting information about the pregnancy and knowledge of the new-born medical status. Pregnancy outcomes must be collected for the female partners of any males who took the IMP(s). Consent to report information regarding these pregnancy outcomes should be obtained from the mother.

Pregnancy itself is not considered as an AE. However, any problem met during the pregnancy should be reported as an AE or a SAE. Spontaneous or induced abortions as well as ectopic pregnancy should be considered as serious. Similarly, any congenital anomaly/birth defect in a child born to a female patient exposed to avelumab and/or TG4001 should be reported as an SAE.

The time period for collecting new pregnancies is from the first administration of the IMP(s) up to 3 months after the last study treatment administration.

Overdose

Any overdose should be reported to Transgene, and documented and followed-up using an “Overdose form”. In addition, any associated symptoms should be reported as an AE or SAE.

9.7. Laboratory values, vital signs, physical findings and other safety data

Laboratory tests results will be recorded on the laboratory results Forms of the eCRF.

Any laboratory result abnormality fulfilling the criteria for a serious adverse event (SAE) should be reported as such, in addition to being recorded as an AE in the eCRF.

Any treatment-emergent abnormal laboratory result which is clinically significant, i.e., meeting one or more of the following conditions, should be recorded as a single diagnosis on the adverse event Form in the eCRF:

- accompanied by clinical symptoms
- leading to a change in study treatments (e.g. cancellation or permanent discontinuation)
- requiring corrective treatment or clinical management

Clinically relevant abnormal laboratory or tests results will be reported by the Investigator and followed until normal or stabilization, or the safety follow-up visit if they are not related to study treatments. They should be recorded on the AE eCRF pages under the signs, symptoms, or diagnosis associated with them.

Clinically relevant abnormal findings in vital signs measurements or physical examinations or ECGs will be reported as AEs or SAEs by the Investigator.

10 STATISTICAL METHODS PLANNED AND SAMPLE SIZE

10.1. Data sets analyzed

Safety population (SAF): all patients included and who received any amount of study treatment will be included in the SAF. Any patient who is assigned a patient number, but does not receive any study treatment will not be included in the SAF.

Evaluable patients' population for DLT determination (DLT population): For the phase Ib of the study, the purpose being to evaluate the safety of the combination, patients must complete the first 4 weeks of the combination or discontinue before the end of the 4 weeks for a DLT to be evaluable for the primary objective of the phase Ib of the study. Patients who are not evaluable for phase Ib safety analysis or are withdrawn for other reasons than toxicity, will be replaced.

Patients must receive at least one dose of both IMPs (TG4001 + avelumab) and have at least one valid post-baseline safety assessment. The statement that a patient had no AE, on the Adverse Events eCRF page, constitutes a valid safety assessment. The occurrence of death also constitutes a valid safety assessment.

Phase II part 1: Evaluable patients' population for tumor response (evaluable per protocol population, EPP): consists of all included patients who were dosed with both IMPs (TG4001 + avelumab) and have at least one baseline and one post-baseline evaluable CT-scan at week 6 after start of study treatment with a best overall response assessment different from 'Unknown' according to RECIST 1.1 evaluation criteria. However, if a patient progressed or died due to underlying cancer before scheduled scan 6 weeks after study treatment start could be performed, the patient will still be included in the evaluable population. Any patient who has a major inclusion/exclusion violation, major dosing violation, or major protocol conduct violation will be excluded from the EPP. Major dosing violation is considered when minimum exposure is not met defined as at least 6 TG4001 injections and 3 avelumab administrations except if patient has progressed or died due to underlying disease before or at the first evaluation. Due to potential abscopal effect when associating radiotherapy and immunotherapy, patients receiving palliative radiotherapy will be analyzed separately. Whatever the reason for withdrawal, except for disease progression and death due to underlying cancer before scheduled scan 6 weeks after study treatment start could be performed, patients considered as non-evaluable for tumor response will be replaced.

Phase II part 2: Full Set Analysis (FAS) will be the primary set for efficacy analyses. It consists of all randomized patients who were administered at least one dose of IMP(s) according to the treatment allocated at randomization.

Evaluable patients' population per protocol (evaluable per protocol population, EPP): consists of all patients from the FAS without any major inclusion/exclusion violation, major dosing violation as defined for phase II part 1, or major protocol conduct violation who were dosed with IMP(s) according to the treatment allocated at randomization and have at least one baseline and one post-baseline evaluable CT-scan at week 6 after start of study treatment with a best overall response assessment different from 'Unknown' according to RECIST 1.1 evaluation criteria.

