Phase II part 1: Evaluable patients' population for tumor response (evaluable per protocol population, EPP): consists of all included patients who were dosed with both IMPs (TG4001 + avelumab) and have at least one baseline and one post-baseline evaluable CT-scan at week 6 after start of study treatment with a best overall response assessment different from 'Unknown' according to RECIST 1.1 evaluation criteria. However, if a patient progressed or died due to underlying cancer before scheduled scan 6 weeks after study treatment start could be performed, the patient will still be included in the evaluable population. Any patient who has a major inclusion/exclusion violation, major dosing violation, or major protocol conduct violation will be excluded from the EPP. Major dosing violation is considered when minimum exposure is not met, defined as at least 6 TG4001 injections and 3 avelumab administrations except if patient has progressed or died due to underlying disease before or at the first evaluation. Due to potential abscopal effect when associating radiotherapy and immunotherapy, patients receiving palliative radiotherapy will be analyzed separately. Whatever the reason for withdrawal, except for disease progression and death due to underlying cancer before scheduled scan 6 weeks after study treatment start could be performed, patients considered as non-evaluable for tumor response will be replaced.

Descriptive statistics will be used. For all analyses, results and graphical representation of data will be presented by dose level and phase II cohort.

No statistical analyses will be performed on safety data. Safety summary tables will include all safety assessments up to 90 days after last study treatment administration.

Phase II part 2:

Full Analysis Set (FAS) will be the primary set for efficacy analyses. It consists of all randomized patients who were administered at least one dose of IMP(s) according to the treatment allocated at randomization.

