TCR	Tumor Cross reactivity
TEAE	Treatment Emergent Adverse Event
TIL	Tumor Infiltrating Lymphocytes
TMF	Trial Master File
TPO	Thyroid Peroxidase
TO	Target Occupancy
ULN	Upper Limit of Normal

VIN

WBC

Vulvar Intraepithelial neoplasia

White Blood Cells

ABBREVIATIONS / DEFINITION OF TERMS (Cont.)

DEFINITIONS

Consented patient	A patient who has signed the informed consent form.
Screened patient	A patient identified during the pre-screening process as a candidate for entry into the study and who has signed the Informed Consent Form (ICF) to undergo procedures required to verify the eligibility criteria before inclusion
Screen Failure	Any patient who underwent screening procedures, and who is found to be not eligible for entry into study and therefore does not receive any study treatment.
Included patient	A patient who signed the ICF, has been included in the study and has received at least one administration of study treatments (TG4001 or avelumab).
Lost of follow-up patient	An included patient for whom no further news is obtained by the Investigator before the last study assessment. The date of lost of follow-up is the date the Investigator received the last news from the patient i.e. during a visit or a telephone contact or any written means.
Protocol deviation	All non adherences to following protocol requirements: study inclusion or exclusion criteria, conduct of the study, patient management or patient assessment.

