Evaluable patients	
Evaluable patients for DLT determination: patients must complete the first 4 weeks of the combination or discontinue before the end of the 4 weeks for a DLT. Patients must receive at least one dose of both IMPs (TG4001 + avelumab) and have at least one valid post-baseline safety assessment.
 
Patients who are not evaluable for phase Ib safety analysis or are withdrawn for other reasons than toxicity, will be replaced.
 
Phase II part 1: Evaluable patients population for tumor response: patients who were dosed with both IMPs (TG4001 + avelumab) and have at least one baseline and one post-baseline evaluable CT-scan at week 6 after start of study treatment with a best overall response assessment different from 'Unknown' according to RECIST 1.1 evaluation criteria and have no major protocol violations or major dosing violations. Major dosing violation is considered when minimum exposure is not met, defined as at least 6 TG4001 injections and 3 avelumab administrations except if patient has progressed or died due to underlying disease before or at the first evaluation.
 
Phase II part 2: Full Analysis Set (FAS) which consists of all randomized patients who were administered at least one dose of IMP(s) according to the treatment allocated at randomization.

Start of study treatment	Corresponds to date of Day 1 for phase Ib and phase II part 1 and to date of randomization for phase II part 2
--------------------------	--

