6.4.2. Randomization

Non applicable for the phase Ib and the phase II part 1.

Randomization is applicable for the phase II part 2.

Upon satisfying all inclusion and exclusion criteria, the Investigator or his/her delegate will proceed to randomization which will be done in the eCRF.

- In patients without liver metastases at baseline randomization will be conducted equally in a 1:1 ratio TG4001 with avelumab (combination arm) versus avelumab alone (monotreatment arm). A stratification will be done on primary tumor site.
- In patients with liver metastases at baseline randomization will be conducted equally in a 1:1 ratio TG4001 with avelumab versus avelumab alone, no stratification will be performed.

The patient must start the study treatment according to allocation during randomization on the day of randomization (+1 day) if randomized into the combination arm and 1 week after randomization (+/- 1 day) if randomized into the monotreatment arm.

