7.7. Post-study follow-up

PFS-FU visit:

For patients who stopped the study treatment for a reason other than progressive disease based on RECIST 1.1 (e.g., AE), tumor evaluation should be obtained every 6 weeks until disease progression by RECIST 1.1 or for a period of 9 months after the start of study treatment. Beyond 9 months, the evaluations will be performed every 12 weeks until disease progression by RECIST 1.1. Tumor measurements will be recorded in the eCRF with the date and method of tumor assessment and the response evaluation in PFS-FU visit. This follow-up should be done even if patients start subsequent antineoplastic therapies.

Further antineoplastic therapies, given after end of study treatment will be reported in the eCRF with the start date and end date.

Tumor sample on biopsy at the time of progressive disease is to be performed for phase II part 2 in patients with accessible lesions at the time of progressive disease.

OS-FU:

From the safety follow-up or last PFS follow-up visit the patient will be followed for survival every 3 months until death (phone call is considered as a follow-up) or until the date of last contact if the patient is lost to follow-up or withdraws consent for collection of long-term data.

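### The part 2 primary set leaves out randomised patients who were never dosed, and control patients have about a week longer in which to fall out; the likely effect is small

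*Combined protocol and SAP*

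**What the plan says.** The synopsis states for part 2: "Full Analysis Set (FAS) will be the primary set for efficacy analyses". Section 10.1 gives the membership rule: "It consists of all randomized patients who were administered at least one dose of IMP(s) according to the treatment allocated at randomization". The definitions table gives the same rule. Sections 10.3.1 and 10.4.2 place the primary PFS log-rank test in this set. Section 10.4.2 also places the OS comparison there, at one-sided 5%.

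Section 6.4.2 starts treatment on the day of randomisation, with one day's grace, for the "combination arm and 1 week after randomization (+/- 1 day) if randomized into the monotreatment arm".

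Sections 10.3.1 and 10.3.2 time PFS and OS from randomisation. Sections 3.1.1 and 3.2 describe part 2 as open label. Section 4.3.3 says that part 2 patients are not replaced.

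The other sets also need dosing. The EPP is drawn from the FAS (Section 10.1). Of the safety set, Section 10.1 says: "Any patient who is assigned a patient number, but does not receive any study treatment will not be included in the SAF".

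On survival follow-up, Section 7.7 says: "From the safety follow-up or last PFS follow-up visit the patient will be followed for survival every 3 months".

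**The concern.** Entry to the primary set depends on something that happens after randomisation, while the endpoint clocks are already running. A randomised patient who leaves before the first dose has time at risk under the endpoint definition but is removed by the set definition. The primary comparison is then not strictly between the groups as randomised.

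The removal need not be balanced. A patient who learns of allocation to control waits about a week before counting; a combination patient counts almost at once. If the reasons for leaving are related to prognosis, the PFS and OS comparisons can shift. With about 80 patients, even one or two exclusions from a single arm would leave an avoidable question over the result.

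**Working it through.** **1. The plan's own figure.** Section 10.2 asks for 76 PFS events for 95% power at one-sided 5%, and 74 in the favourable zone. Section 3.2 gives medians of 4.5 and 2.0 months, so HR = 2.0/4.5 = 0.444. Freedman: (1.645 + 1.645)² × [(1 + 0.444)/(1 − 0.444)]² ≈ 10.82 × 6.76 ≈ 73.2, rounded up to 74. This matches 74 and is within 2 of 76. The choice of analysis set does not change the event target.

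**2. Pre-dose windows (Section 6.4.2).** Combination: 0 to 0 + 1 = 1 day. Control: 7 − 1 = 6 to 7 + 1 = 8 days.

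**3. One product or both?** The wording of the FAS does not settle this. Three places favour one product: the definitions table counts a patient as included after either product; the part 1 set in Section 10.1 says explicitly that both are needed; and the part 2 disposition list in Section 10.5.2 counts as treated anyone given either or both. If both were required, the windows would be similar, because avelumab starts on Day 8 in both arms (Section 7.3). Membership would still depend on dosing.

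**4. Which sets cover undosed patients?**

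| Set | Named for part 2 efficacy in | Includes undosed? |
|---|---|---|
| FAS | 10.3.1, 10.4.2 | No |
| EPP (subset of FAS) | 10.3.1, 10.4.2 | No |
| SAF | 10.4.2 | No |

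**5. Expected losses.** The documents give no pre-dose loss rate, so a monthly rate r of 1-10% is assumed. With 84/2 = 42 randomised per arm (Section 10.2), the loss over d days is 42 × [1 − (1 − r)^(d/30.44)].

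- Control, d = 7: 0.10 (r = 1%), 0.49 (5%), 1.01 (10%).
- Control, r = 10%, d = 6 to 8: 0.86 to 1.15.
- Combination, r = 10%, d = 0 to 1: 0 to 0.15.
- Check against the plan: 5% drop-out is 0.05 × 42 = 2.1 per arm in total. Seven days are 7/30.44 = 0.23 month. Spread evenly over 3 months (assumed) this gives 2.1 × 0.23/3 = 0.16; over the 26 months in Section 10.2 it gives 0.02. Two lost before dosing would use up the control arm's whole allowance, (84 − 80)/2 = 2, so 2 is treated as a ceiling.

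**6. Effect on the PFS test (simulation).** 40 per arm, exponential PFS, accrual of 2 a month, events placed on the 6-weekly scan grid (12-weekly after 36 weeks), cut at 69 events (Section 3.2), unstratified one-sided 5% log-rank, interim and adaptation ignored. Under the null both medians are 2.0 months, with a 50:50 baseline factor of assumed HR 2. Losses occur in control only.

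| Controls lost | Type I error, 0 / 1 / 2 lost |
|---|---|
| At random | 5.2% / 5.2% / 5.1% |
| From the better-prognosis half | 5.2% / 5.6% / 6.0% |
| Earliest failures | 5.2% / 4.3% / 3.6% |

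The first row uses 40,000 runs for the losses and the other rows 100,000, where the Monte Carlo standard error is √(0.05 × 0.95/100,000) ≈ 0.07 points. Better-half loss with HR 1.5 gives 5.2%, 5.5% and 5.8%; with HR 3 it gives 5.4%, 5.9% and 6.6%. Power at the planned medians falls from 94.6% to 93.9% or 92.9% if the 1 or 2 earliest failures are lost.

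**7. Effect on OS.** With assumed OS medians of about 9 to 19 months and HR 2, type I error is 5.1-5.2% with nobody lost, 5.4-5.7% with one better-prognosis control lost and 5.8-6.2% with two.

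**The case against.** Much of the case against stands.

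- **Follow-up.** A reader might infer from Section 7.7 that a never-dosed patient is not followed at all, having no safety or PFS visit to start from. The documents do not support this. Appendix IV follows all patients off treatment for survival every 3 months, Section 8 runs part 2 efficacy observation from randomisation, the definitions table sets the part 2 start of study treatment at randomisation, and Section 3.1.1 follows all patients. What remains is a loose starting point in 7.7.
- **Disposition.** Section 10.5.2 already asks for exclusions with reasons, for each population and by arm. Only an explicit line for the number randomised is missing.
- **Harm.** A reader might infer that the rule favours the combination arm. That needs every lost control to come from the better-prognosis group and nobody to be lost from combination, and no passage says so. Selecting on realised PFS would give about 6% or 7% for one or two lost, but those times are unknown at Day 7, so these are upper bounds.
- **Limited gain for PFS.** Under the censoring rule in Sections 10.3.1 and 10.4.2, an undosed control who starts other therapy before a scan is censored near time zero. In the log-rank test that is the same as being dropped.
- **Timing.** Sections 3.1.2 and 3.2 describe the interim look and sample-size adjustment as done, and the design combines stages by the Cui-Hung-Wang method. Changing the primary set now is more than a wording change.
- **Hidden text.** Redactions follow the PFS and OS test statements in Section 10.4.2, and the SAP named in Sections 10.2 and 10.6 is not in the text provided. Either could hold an all-randomised analysis.

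None of this alters the visible definition of the primary set, or the unequal windows on the likelier reading.

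**Conclusion.** The point holds as a minor one. The visible primary set is conditional on dosing, the window for falling out is 0-1 day against 6-8 days on the one-product reading, and no visible part 2 analysis includes everyone randomised. It cannot be said that no such analysis exists.

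The likely loss is 0-1 control. One adversely selected control adds about 5.6 − 5.2 = 0.4 percentage points to the PFS type I error. Random loss adds nothing, and loss of early failures is conservative. These sizes rest on an assumed loss rate, an assumed prognostic hazard ratio and a simulation without the adaptive step. The direction cannot be fixed from the documents, so this is not a finding that the trial is biased towards the combination. The case for change is that the safeguard is cheap.

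**What to change.** 1. Analyse PFS and OS in all randomised patients without liver metastases at baseline, in the arm assigned, dosed or not. Keep the dosed set as a sensitivity analysis.
2. State whether any patient randomised before the interim look was undosed. If none was, the stage-1 statistic is unaffected by those patients and the all-randomised set can be primary. If some were, keep the stage-1 statistic as computed and report the all-randomised log-rank as a pre-specified analysis beside the FAS result.
3. Add a line for the number randomised to the part 2 disposition table in Section 10.5.2.
4. Align Section 7.7 with Section 3.1.1, Section 8 and Appendix IV, so that survival contacts for a never-dosed patient start from randomisation.
5. Leave the censoring rule at further therapy unchanged. It limits what is recovered for PFS. For OS the gain is direct, because OS is censored only at last contact.

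The cost is wording in the synopsis, the definitions table and Sections 7.7, 10.1, 10.3.1 and 10.5.2, one extra analysis run, and documentation of a change made after the interim. Event targets stay as they are.
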